3. STATISTICAL SOFTWARE

All statistical outputs (summary tables and data listings) will be generated using SAS® version 9.4 or further.

CONFIDENTIEL / CONFIDENTIAL

Toute reproduction ou distribution, totale ou partielle, de ce document, sans autorisation préalable de ICON PLC est interdite.
Reproduction and distribution of this document, in whole or in part, is strictly forbidden without prior authorization from ICON PLC.

	STATISTICAL ANALYSIS PLAN	FARAPULSE PersAFOne SAP V1.0 PERSAFONE Page 32 /49
---	----------------------------------	--

4. STATISTICAL TABLES, LISTINGS AND GRAPHS (TABLE OF CONTENTS)

4.1. Statistical Tables

4.1.1. Table 1. Subject enrollment per Site

		Enrolled patients	ITT patients	PP patients
		(N=XX)	(N=XX)	(N=XX)
Site #	Site Name			
XX		XX (XX%)	XX (XX%)	XX (XX%)
XX		XX (XX%)	XX (XX%)	XX (XX%)

4.1.2. Table 2. Demographics

		ITT Population	
		N = XX	
		Mean±S.D.	
		Median (min, max)	[95% CI]
		(Q1, Q3)	
Age		XX±X XX (XX, XX) (XX, XX)	[XX - XX]
BMI		XX±X XX (XX, XX) (XX, XX)	[XX - XX]
		n/N (%)	[95% CI]
Male Gender		XX/XX (XX.X%)	[XX% - XX%]

CONFIDENTIEL / CONFIDENTIAL

Toute reproduction ou distribution, totale ou partielle, de ce document, sans autorisation préalable de ICON PLC est interdite.
Reproduction and distribution of this document, in whole or in part, is strictly forbidden without prior authorization from ICON PLC.

STATISTICAL ANALYSIS PLAN

FARAPULSE PersAFOne SAP V1.0

PERSAFONE

Page 33 /49

Female Gender

XX/XX (XX.X%)

[XX - XX%]

4.1.3. Table 3. Baseline Medical History

	ITT Population	
	Mean±S.D.	Median (min, max) (Q1, Q3)
	XX±X XX (XX, XX) (XX, XX)	[95% CI]
Left atrial diameter (cm)	XX±X XX (XX, XX) (XX, XX)	[XX - XX]
AF history (number of months)	XX±X XX (XX, XX) (XX, XX)	[XX - XX]
LVEF (%)	XX±X XX (XX, XX) (XX, XX)	[XX - XX]
CHA2DS2VASC	XX±X XX (XX, XX) (XX, XX)	[XX - XX]
	n/N (%)	[95% CI]
Patient that failed any AAD	XX/XX (XX.X%)	[XX% - XX%]
If Yes: Class I	XX/XX (XX.X%)	[XX% - XX%]

CONFIDENTIEL / CONFIDENTIAL

Toute reproduction ou distribution, totale ou partielle, de ce document, sans autorisation préalable de ICON PLC est interdite.
Reproduction and distribution of this document, in whole or in part, is strictly forbidden without prior authorization from ICON PLC.

STATISTICAL ANALYSIS PLAN

FARAPULSE PersAFOne SAP V1.0

PERSAFONE

Page 34 /49

If Yes: Beta Blocker/Class II	XX/XX (XX.X%)	[XX% - XX%]
If Yes: Class III	XX/XX (XX.X%)	[XX% - XX%]
If Yes: Calcium Channel Blocker/Class IV	XX/XX (XX.X%)	[XX% - XX%]
Smoking	XX/XX (XX.X%)	[XX% - XX%]
Dyslipidemia	XX/XX (XX.X%)	[XX% - XX%]
COPD	XX/XX (XX.X%)	[XX% - XX%]
PPM/ICD	XX/XX (XX.X%)	[XX% - XX%]
Unstable angina	XX/XX (XX.X%)	[XX% - XX%]
NYHA Heart Failure	XX/XX (XX.X%)	[XX% - XX%]
Class I	XX/XX (XX.X%)	[XX% - XX%]
Class II	XX/XX (XX.X%)	[XX% - XX%]
Class III	XX/XX (XX.X%)	[XX% - XX%]
Class IV	XX/XX (XX.X%)	[XX% - XX%]
Any History of Structural heart disease	XX/XX (XX.X%)	[XX% - XX%]
If yes: Cardiomyopathy	XX/XX (XX.X%)	[XX% - XX%]
If yes: Coronary artery disease	XX/XX (XX.X%)	[XX% - XX%]
If yes: Aneurysm	XX/XX (XX.X%)	[XX% - XX%]
If yes: Left ventricular hypertrophy	XX/XX (XX.X%)	[XX% - XX%]
If yes: Valvular heart disease	XX/XX (XX.X%)	[XX% - XX%]
Cerebrovascular disease	XX/XX (XX.X%)	[XX% - XX%]
If yes: CVA/Stroke	XX/XX (XX.X%)	[XX% - XX%]
If yes: TIA	XX/XX (XX.X%)	[XX% - XX%]
Cardiac surgery	XX/XX (XX.X%)	[XX% - XX%]
If yes: CABG	XX/XX (XX.X%)	[XX% - XX%]
If yes: Valve	XX/XX (XX.X%)	[XX% - XX%]
Diabetes	XX/XX (XX.X%)	[XX% - XX%]

CONFIDENTIEL / CONFIDENTIAL

Toute reproduction ou distribution, totale ou partielle, de ce document, sans autorisation préalable de ICON PLC est interdite.
Reproduction and distribution of this document, in whole or in part, is strictly forbidden without prior authorization from ICON PLC.

STATISTICAL ANALYSIS PLAN

FARAPULSE PersAFOne SAP V1.0

PERSAFONE

Page 35 /49

Hypertension	XX/XX (XX.X%)	[XX% - XX%]
Hyperthyroidism	XX/XX (XX.X%)	[XX% - XX%]
Hypothyroidism	XX/XX (XX.X%)	[XX% - XX%]
Myocardial infarction	XX/XX (XX.X%)	[XX% - XX%]
Peripheral vascular disease	XX/XX (XX.X%)	[XX% - XX%]
Pulmonary hypertension	XX/XX (XX.X%)	[XX% - XX%]
Renal dysfunction/failure	XX/XX (XX.X%)	[XX% - XX%]
Sleep apnea	XX/XX (XX.X%)	[XX% - XX%]

4.1.4. Table 4. Procedure

	ITT Population	
	N = XX	
	Mean±S.D.	[95% CI]
Procedure time (hours)	Mean±S.D. Median (min, max) (Q1, Q3)	[95% CI]
Farawave dwell time (hours)	XX±X XX (XX, XX) (XX, XX)	[XX - XX]
PVI ablation time (hours)	XX±X XX (XX, XX) (XX, XX)	[XX - XX]

CONFIDENTIEL / CONFIDENTIAL

Toute reproduction ou distribution, totale ou partielle, de ce document, sans autorisation préalable de ICON PLC est interdite.
Reproduction and distribution of this document, in whole or in part, is strictly forbidden without prior authorization from ICON PLC.

ICON	STATISTICAL ANALYSIS PLAN	FARAPULSE PersAFOne SAP V1.0 PERSAFONE Page 36 /49
-------------	----------------------------------	--

	(XX, XX)	
CTI (FARAFLEX) dwell time (hours)	XX±X XX (XX, XX) (XX, XX)	[XX - XX]
LAPW ablation time (hours)	XX±X XX (XX, XX) (XX, XX)	[XX - XX]
Fluoroscopy time (min)	XX±X XX (XX, XX) (XX, XX)	[XX - XX]
Contrast volume (cc)	XX±X XX (XX, XX) (XX, XX)	[XX - XX]
IV fluid volume (cc)	XX±X XX (XX, XX) (XX, XX)	[XX - XX]
Total number of PVI applications	XX	NA
Number of applications/patient	XX±X XX (XX, XX) (XX, XX)	[XX - XX]
Number of applications/vein	XX	NA

CONFIDENTIEL / CONFIDENTIAL

Toute reproduction ou distribution, totale ou partielle, de ce document, sans autorisation préalable de ICON PLC est interdite.
Reproduction and distribution of this document, in whole or in part, is strictly forbidden without prior authorization from ICON PLC.

ICON	STATISTICAL ANALYSIS PLAN	FARAPULSE PersAFOne SAP V1.0 PERSAFONE Page 37 /49
-------------	----------------------------------	--

Number of LAPW applications	XX	NA
	N, n, n/N (%)	95% CI
Total number of veins treated	XX	NA
Total number of veins isolated	XX	NA
Of the total number of veins treated, the number of veins isolated	XX/XX (XX.X%)	[XX% - XX%]
CTI acute isolation	XX/XX (XX.X%)	[XX% - XX%]
Total number of CTI applications	XX	NA

4.1.5. Table 5. Remap at 75 Days

	ITT Population N = 25	
	Mean±S.D. Median (min, max) (Q1, Q3)	[95% CI]
Days follow up at remap	XX±X XX (XX, XX) (XX, XX)	[XX - XX]
	n/N (%)	[95% CI]
Durable PVI	XX/XX (XX.X%)	[XX% - XX%]
LSPV chronic isolation	XX/XX (XX.X%)	[XX% - XX%]
LIPV chronic isolation	XX/XX (XX.X%)	[XX% - XX%]
LCPV chronic isolation	XX/XX (XX.X%)	[XX% - XX%]
RSPV chronic isolation	XX/XX (XX.X%)	[XX% - XX%]
RIPV chronic isolation	XX/XX (XX.X%)	[XX% - XX%]
RMPV chronic isolation	XX/XX (XX.X%)	[XX% - XX%]

CONFIDENTIEL / CONFIDENTIAL

Toute reproduction ou distribution, totale ou partielle, de ce document, sans autorisation préalable de ICON PLC est interdite.
Reproduction and distribution of this document, in whole or in part, is strictly forbidden without prior authorization from ICON PLC.

ICON	STATISTICAL ANALYSIS PLAN	FARAPULSE PersAFOne SAP V1.0 PERSAFONE Page 38 /49
-------------	----------------------------------	--

CTI chronic isolation	XX/XX (XX.X%)	[XX% - XX%]
LAPW chronic isolation	XX/XX (XX.X%)	[XX% - XX%]

4.1.6. Table 6. Per Remapped Veins Analysis

	Veins Remapped N = XX	
	n/N (%)	[95% CI]
Number of veins durably isolated	XX/XX (XX.X%)	[XX% - XX%]
Number of veins with gaps	XX/XX (XX.X%)	[XX% - XX%]
Missing Data	XX	NA

4.1.7. Table 7. Arrhythmia Recurrence at 12 Months

	ITT Population N = XX	
	Mean±S.D. Median (min, max) (Q1, Q3)	[95% CI]
TTM compliance	XX±X XX (XX, XX) (XX, XX)	[XX - XX]
	n/N (%)	[95% CI]
Holter compliance (6 month)	XX/XX (XX.X%)	[XX% - XX%]
Freedom from AF/AFL/AT	XX/XX (XX.X%)	[XX% - XX%]
	XX/XX (XX.X%)	[XX% - XX%]
On AADs	XX/XX (XX.X%)	[XX% - XX%]

CONFIDENTIEL / CONFIDENTIAL

Toute reproduction ou distribution, totale ou partielle, de ce document, sans autorisation préalable de ICON PLC est interdite.
Reproduction and distribution of this document, in whole or in part, is strictly forbidden without prior authorization from ICON PLC.

	STATISTICAL ANALYSIS PLAN	FARAPULSE PersAFOne SAP V1.0 PERSAFONE Page 39 /49
---	----------------------------------	--

Off AADs		
Freedom from AF	XX/XX (XX.X%)	[XX% - XX%]
	XX/XX (XX.X%)	[XX% - XX%]
On AADs	XX/XX (XX.X%)	[XX% - XX%]
Off AADs	XX/XX (XX.X%)	[XX% - XX%]
Freedom from AF/AFL/AT, no DCCV>90 days, no RF, no ablation >90 days	XX/XX (XX.X%)	[XX% - XX%]
On AADs	XX/XX (XX.X%)	[XX% - XX%]
Off AADs	XX/XX (XX.X%)	[XX% - XX%]
Freedom from AF, no DCCV>90 days, no RF, no ablation >90 days	XX/XX (XX.X%)	[XX% - XX%]
On AADs	XX/XX (XX.X%)	[XX% - XX%]
Off AADs	XX/XX (XX.X%)	[XX% - XX%]

4.1.8. Table 8. Primary Safety Endpoint –Composite Safety Endpoint (CSE)

	ITT Population N = XX	
	n/N (%)	[95% CI]
Early and Late Onset Composite Safety Endpoint	XX/XX (XX.X%)	[XX% - XX%]
Total Early (within 30 days of Index or Remap Procedure)	XX/XX (XX.X%)	[XX% - XX%]
Death	XX/XX (XX.X%)	[XX% - XX%]
Myocardial infarction (MI)	XX/XX (XX.X%)	[XX% - XX%]
Persistent diaphragmatic paralysis	XX/XX	[XX% - XX%]

CONFIDENTIEL / CONFIDENTIAL

Toute reproduction ou distribution, totale ou partielle, de ce document, sans autorisation préalable de ICON PLC est interdite.
Reproduction and distribution of this document, in whole or in part, is strictly forbidden without prior authorization from ICON PLC.

Stroke	(XX.X%)	
Transient ischemic attack (TIA)	XX/XX (XX.X%)	[XX% - XX%]
Peripheral or organ thromboembolism	XX/XX (XX.X%)	[XX% - XX%]
Pericarditis	XX/XX (XX.X%)	[XX% - XX%]
Cardiac tamponade / perforation	XX/XX (XX.X%)	[XX% - XX%]
Vascular access complications requiring intervention	XX/XX (XX.X%)	[XX% - XX%]
Heart block	XX/XX (XX.X%)	[XX% - XX%]
Total Late (any time during follow-up through 12 months)	XX/XX (XX.X%)	[XX% - XX%]
Pulmonary vein (PV) stenosis (> 70% diameter reduction from baseline)	XX/XX (XX.X%)	[XX% - XX%]
Atrio-esophageal fistula	XX/XX (XX.X%)	[XX% - XX%]

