PLANNED PROCEDURE:	
Index Procedure:
 
Subjects will undergo an attempt to isolate all pulmonary veins or their anatomic equivalent.Subjects with a past history of atrial flutter, who are at risk of atrial flutter, who present with atrial flutter during the Index Procedure or who have inducible cavotricuspid isthmus-mediated (typical) flutter may undergo ablation of the cavo-tricuspid isthmus at the discretion of the investigator.Additional left atrial lesions may be made at the discretion of the investigator including focal sites, electrical gaps and lines of isolation. 
75-Day Remap Procedure:
 
Subjects will undergo a remapping procedure at 75 ± 15 days to assess the durability of the ablation lesions performed during the Index Procedure.During this procedure, additional ablations may be made at the discretion of the investigator to optimize patient outcomes.

PRIMARY SAFETY ENDPOINT:	
The primary safety endpoint for this study is the Composite Safety Endpoint (CSE) defined as the incidence of the following early-onset and late-onset serious adverse events (SAEs) which are device- or procedure-related, as adjudicated by the CEDMC. (See Table 4. Composite Safety Endpoint Definitions in Section 6.1).
 
Early onset (within 30 days of an Index or Remap Procedure)
 
• Death• Myocardial infarction (MI)• Persistent diaphragmatic paralysis• Stroke or transient ischemic attack (TIA)• Peripheral or organ thromboembolism• Pericarditis• Cardiac tamponade / perforation• Vascular access complications requiring intervention• Heart block 
Late onset (any time during follow-up through 12 months)
 
• Pulmonary vein (PV) stenosis (> 70% diameter reduction from baseline)• Atrio-esophageal fistula
SECONDARY SAFETY ENDPOINTS:	
1. The Primary Safety Endpoint assessed at 7 days2. The proportion of subjects with a device- or procedure-related SAE3. The proportion of subjects with stroke or TIA4. The proportion of subjects requiring cardioversion5. The proportion of subjects requiring an arrhythmia-related (AF, AFL or AT) hospitalization

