3.1 Study Objective

The objective of this safety and feasibility study is to assess whether the endocardial creation of electrically nonconductive lesions via PEF catheter ablation applied using the FARAPULSE Endocardial Multi Ablation System is a feasible and safe treatment for PersAF and associated AFL.

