- Event Monitor: An Event Monitor and training will be provided to the subject, to be used for weekly scheduled and ad hoc symptomatic monitoring through the remainder of study follow-up. (**See Section 3.11.4, Arrhythmia Core Lab**). If necessary patients will be provided with an Event Monitor by mail, telephonic training and successful transmission of a monitoring record.
- AFD Management: For patients who do not require reablation during the 75-Day remap visit AFD may be stopped at the investigator's discretion.

The following data will be collected from all subjects at 75 ± 15 days:

- Adverse Events
- Symptoms of recurrent arrhythmia
- Fluoroscopic examination of diaphragm motion is required if:
 - Patient underwent remapping to assess phrenic nerve response
 - The patient declined a remap procedure but the post Index Procedure fluoroscopic examination indicated diminished phrenic nerve response
- Data regarding the use, changes in or discontinuation of anticoagulation, rate control and/or antiarrhythmic medications.
- Pregnancy test (all women of child-bearing potential) prior to remap
- Cardiac rhythm as determined by a 12-lead ECG
- Cardiac CT or MRI scan to assess the patency of the pulmonary veins
- Cardioversions, ablations or hospital admissions since last visit
- Heart failure status as assessed by NYHA classification at the time of visit

3.12.6 6-Month Visit

Subjects will return for an office visit 6 months (180 days \pm 30 days) following the Index Procedure. The following data will be collected at the 6-Month Visit:

- Adverse Events
- Symptoms of recurrent arrhythmia
- If either the post-Index Procedure or post-75-Day Remap Procedure fluoroscopies indicated diminished phrenic nerve response, and resolution has not been previously demonstrated, a repeat fluoroscopic examination. Females of childbearing potential undergoing this examination will also receive a pregnancy test prior.
- Data regarding the use, changes in or discontinuation of anticoagulation, rate control and/or antiarrhythmic medications
- Cardiac rhythm as determined by a 12-lead ECG at the time of the visit
- Arrhythmia assessment (See **Section 3.11.4, Arrhythmia Core Lab**).
 - A 24-hour continuous ECG monitor and training will be provided to the subject
 - Event Monitor compliance will be reviewed for weekly scheduled and ad hoc symptomatic monitoring and retraining of the subject provided as needed
- Cardioversions, ablations or hospital admissions since last visit

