6.1 Primary Safety Endpoint

The primary safety endpoint for this study is the Composite Safety Endpoint (CSE) defined as the incidence of the following early-onset and late-onset serious adverse events (SAEs) which are device- or procedure-related, as adjudicated by the CEDMC and defined below in **Table 4. Composite Safety Endpoint Definitions**.

Early onset (within 30 days of an Index or Remap Procedure)

- Death
- Myocardial infarction (MI)
- Persistent diaphragmatic paralysis
- Stroke or transient ischemic attack (TIA)
- Peripheral or organ thromboembolism
- Pericarditis
- Cardiac tamponade / perforation
- Vascular access complications requiring intervention
- Heart block

Late onset (any time during follow-up through 12 months)

- Pulmonary vein (PV) stenosis (> 70% diameter reduction from baseline)
- Atrio-esophageal fistula

Table 4. Composite Safety Endpoint Definitions

Adverse Event	Description/Criteria
Death	Death
Myocardial infarction (MI)	Myocardial infarction will be demonstrated by any one of the following: 1) detection of ECG changes indicative of new ischemia (new ST-T wave changes or new LBB) that persist for more than 1 hour. 2) development of new pathological Q waves on an ECG 3) imaging evidence of new loss of viable myocardium or new regional wall motion abnormality
Persistent diaphragmatic paralysis	Diaphragmatic paralysis: Change from baseline diaphragmatic function as demonstrated radiographically by elevation of the diaphragm above the normal range but not due to a pulmonary process such as atelectasis. Permanent: not resolved by completion of study follow-up
Stroke or transient ischemic attack (TIA)	Stroke is an acute symptomatic episode of neurological dysfunction attributed to a vascular cause (ischemia or hemorrhage) in which symptoms last more than 24 hours, or if symptoms last less than 24 hours, a brain imaging study demonstrates infarction. Transient ischemic attack is a new focal neurological deficit with rapid symptom resolution always within 24 hours.

Adverse Event	Description/Criteria
Peripheral or organ thromboembolism	Formation in a blood vessel of a clot (thrombus) that results from the breaking loose of all or part of an existing thrombus, which is then carried by the blood to lodge in/occlude a more distal vascular site.

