2.3. Analysis Sets

2.3.1. Definition of patient populations

3 populations will be defined:

- The Enrolled population will include all subjects who provided their informed consent.
- The Safety / Intent-to-Treat (ITT) population will include all enrolled subjects except those who terminate their participation prior to the beginning of the Index Procedure.
- The Per Protocol (PP) population will include Intent-to-treat subjects for whom the Index Procedure is finished without interfering investigational device deficiency or malfunction.

The choice of reported analysis on ITT or PP populations will be driven by the purposes of the analysis.

In any case, the primary feasibility endpoint will be assessed on the ITT and PP populations.

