2.4.8. Safety Endpoint

Descriptive statistical data is used to analyze the Primary Safety Endpoint (PSE), the secondary safety endpoints and others analysis. The analysis is performed on the ITT populations.

The Safety endpoint will be performed on the ITT population and will include

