- Derived criteria “Stroke after index procedure” will be defined as follows:
IF Event name='STROKE' in **Adverse event form** **AND** Event start date ≥ Procedure date in **Procedural data Form (PR)** **THEN** STROKE='Yes'
ELSE STROKE='No'
- Derived criteria “Transient Ischemic Attack (TIA) after index procedure” will be defined as follows:
IF Event name=' Transient Ischemic Attack' in **Adverse event form** **AND** Event start date ≥ Procedure date in **Procedural data Form (PR)** **THEN** TIA='Yes'
ELSE TIA='No'
- Derived criteria “Stroke after Remap procedure” will be defined as follows:
IF Event name='STROKE' in **Adverse event form** **AND** Event start date ≥ Remap date IN **FOLLOW-UP 3D ELECTROANATOMICAL MAPPING FORM (RM)** **THEN** STROKE='Yes'
ELSE STROKE='No'
- Derived criteria “Transient Ischemic Attack (TIA) after Remap procedure” will be defined as follows:
IF Event name=' Transient Ischemic Attack' in **Adverse event form** **AND** Event start date ≥ Remap date in **FOLLOW-UP 3D ELECTROANATOMICAL MAPPING FORM (RM)** **THEN** TIA='Yes'
ELSE TIA='No'
- Derived criteria “Arrhythmia-related (AF, AFL, AT) hospitalization” will be defined as follows:
IF Arrhythmia-related (AF, AFL, AT) hospitalization ='Yes' in **MDT excel file** **THEN** Arrhythmia-related (AF, AFL, AT) hospitalization ='Yes'
ELSE IF Arrhythmia-related (AF, AFL, AT) hospitalization ='No' in **MDT excel file** **THEN** Arrhythmia-related (AF, AFL, AT) hospitalization ='No'
- Derived criteria “Death” will be defined as follows:
IF SAE: Death='Yes' in **Adverse event form** **OR** Reason ='Patient death' in **study exit form** **THEN** Death='Yes'
ELSE Death='No'

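### No planned safety table separates early events after the index ablation from those after the durability remap

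*SAP*

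**What the plan says.** Protocol 6.1 defines the early component of the CSE as "Early onset (within 30 days of an Index or Remap Procedure", and SAP 2.4.8.1 repeats it. SAP 2.5 codes each early component as an OR of two date conditions, one against the index date and one against the remap date. Table 8 has a single early total, "Total Early (within 30 days of Index or Remap Procedure", and Table 12 repeats the pooled layout for the 7-day version.

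The denominator is fixed by SAP 2.4.8: "The Safety endpoint will be performed on the ITT population and will include". That population "will include all enrolled subjects except those who terminate their participation prior to the beginning of the Index Procedure" (SAP 2.3.1), so it is set by the index procedure alone.

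The Executive Summary of the protocol gives the reason for the second procedure: "Subjects will undergo a remapping procedure at 75 ± 15 days to assess the durability of the ablation lesions performed during the Index Procedure". The same row allows further ablation at that time. Protocol 3.12.5 foresees the case "The patient declined a remap procedure". Protocol 3.1 states the objective as whether the ablation "is a feasible and safe treatment for PersAF and associated AFL".

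The only derivations that separate the procedures are for stroke and TIA. SAP 2.5 has "Stroke after index procedure", its TIA counterpart, and matching after-remap variables. Table 12 shows one stroke row and one TIA row, without that split.

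**The concern.** The objective concerns the safety of a treatment. The remap repeats, as far as the investigator judges necessary, the index steps of venous and transseptal access (Protocol 3.11.1 and 3.11.2), so it has access and perforation risks of its own. A tamponade or groin complication at the remap enters the same row as one from the index ablation. A reader of Table 8 cannot tell which procedure produced the events, and subjects who were never remapped remain in the denominator although they were never at risk in the second window.

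At stake is how the results can be used. Protocol 5.3 says that they will inform further studies, and Protocol 1.4 names a CE Mark trial. Planning such a trial needs risk per procedure. The prior-study summaries in Protocol 1.3 place the tamponade, the air embolism and the groin fistulae at the index procedure or index hospitalization, so a pooled rate is not directly comparable with them.

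**Working it through.** The plan states no expected safety rate, threshold or margin, so there is no figure to reproduce. The per-procedure risks below are assumptions.

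**1. Do the two windows overlap?** Index window: days 0 to 30. Remap visit: 75 − 15 = day 60 to 75 + 15 = day 90, with its window ending at the latest on 90 + 30 = day 120. The gap between the windows is at least 60 − 30 = 30 days. They would meet only if a remap took place by day 30. Early events can therefore be assigned to one procedure by date.

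**2. How many are remapped?** In the two prior studies, 35/40 = 87.5% and 49/60 = 81.7% had returned for remapping (Protocol 1.3.1 and 1.3.2; follow-up may have been incomplete). I use 80% to 100%.

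**3. Expected pooled rate.** With index risk p, remap risk q, share remapped r, and independence, pooled = 1 − (1 − p)(1 − rq).

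| p | q | r | Pooled | Pooled / p |
|---|---|---|---|---|
| 5% | 1% | 0.80 | 1 − 0.95 × 0.992 = 5.76% | 1.15 |
| 2% | 2% | 1.00 | 1 − 0.98 × 0.98 = 3.96% | 1.98 |
| 5% | 5% | 1.00 | 1 − 0.95 × 0.95 = 9.75% | 1.95 |
| 2% | 5% | 1.00 | 1 − 0.98 × 0.95 = 6.90% | 3.45 |

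The chance of at least one remap event is 1 − (1 − q)^n. It is 27.5% for q = 1% and n = 32, and 87.1% for q = 5% and n = 40.

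**4. What the tables would show.** Take one index event and one remap event in different subjects. Intervals are exact (Clopper–Pearson), which SAP 2.1.4 prescribes when the asymptotic assumptions fail and the proportion is neither 0% nor 100%.

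| | N = 40 | N = 25 (printed in Tables 5 and 19) |
|---|---|---|
| Pooled, ITT | 2/40 = 5.0% (0.6–16.9) | 2/25 = 8.0% (1.0–26.0) |
| Index only, ITT | 1/40 = 2.5% (0.1–13.2) | 1/25 = 4.0% (0.1–20.4) |
| Remap, 87.5% remapped | 1/35 = 2.9% (0.1–14.9) | 1/22 = 4.5% (0.1–22.8) |

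With no index event and one remap event at N = 40, the pooled row reads 2.5% (0.1–13.2), while the index rate is 0% (Agresti–Coull 0–10.4).

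**5. Can the SAP code support a split?** Not as printed. SAP 2.5 writes the early condition as `30≤` the days since the procedure, and `7≤` for the 7-day version. Read literally, these select events on or after that day. An event on day 3 after the index procedure fails. An event 5 days after a day-75 remap is on day 75 + 5 = 80 from index and meets the index condition. The split would be wrong in both directions.

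**The case against.** The pooling is prespecified in the protocol, reproduced in the SAP and visible in the row label. It can only raise the headline rate, which is the cautious direction for safety. Protocol 5.3 sets no hypothesis, so no decision rule changes. These points stand, and they are why the pooled CSE should remain primary.

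The remap is also not purely a research procedure. Further ablation is allowed there, Protocol 3.11.3 permits one repeat ablation in the Blanking Period without a Therapeutic Failure, and chronic success has a reablated category. The pooled rate is a fair safety measure for that whole strategy. This stands too, and it is the reason to show the remap row with and without reablation.

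On the denominator, Table 8 reports no remap rate, so no reported remap rate is wrong. One is simply absent. The prior-study summaries attribute no complication explicitly to the 35 + 49 = 84 remaps, although they do not date every rehospitalization. The true inflation may therefore lie towards the low end of the range.

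A reader might infer that the open-ended after-index stroke and TIA rules should be closed at the remap date. The documents do not support that. Protocol 6.2 asks for the proportion with stroke or TIA without a procedure window, and closing the rule would remove post-remap events from the variable that serves this endpoint.

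**Conclusion.** The point holds as a gap in planned reporting. The early CSE pools two procedures on one ITT denominator, and no planned table gives either the early rate of the index treatment or a rate among the subjects remapped. The pooled rate is about 1.15 to 3.45 times the index rate, given index risk 2–5%, remap risk 1–5%, 80–100% remapped, and independence. None of these risks is in the documents.

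Two stronger readings go too far. One is that the trial cannot state how safe the index treatment is. It can, because the windows are disjoint for an on-schedule remap, events are dated, and listings of primary safety endpoints and SAEs are planned (SAP 4.2). The other is that pooling doubles the rate. That needs equal risk at both procedures and every subject remapped.

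With so few events expected, a split chosen after seeing them would carry less weight than one written down now. This is a worthwhile, inexpensive improvement to a descriptive analysis.

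**What to change.** 1. Correct the `30≤` and `7≤` conditions in SAP 2.5 so that they select events from the procedure date up to the stated day. Do this before programming any split.
2. Keep the pooled CSE as primary. Add to Table 8 (30 days) and Table 12 (7 days) descriptive rows for early CSE in the index window, over ITT, and early CSE in the remap window, over remapped subjects, shown with and without reablation. Footnote that a subject with an event in both windows counts once in the pooled row and once in each new row, so the rows need not add up.
3. Leave the overall stroke/TIA endpoint open through follow-up. If a split is wanted, add a separate variable for events after index and before remap. State that never-remapped subjects are evaluable for it, because the general rule at the start of SAP 2.5 would otherwise set them to missing for want of a remap date.

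The dates are already on the procedure and remap forms, so the cost is a few rows and some date logic. The new rows will be sparse with wide intervals. Late-onset PV stenosis and atrio-esophageal fistula cannot be assigned by window and stay pooled. Any remap outside 75 ± 15 days needs checking by hand.
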